**A Double-Blind, Placebo-Controlled Study of Dronabinol in Trichotillomania and Other
Body focused Repetitive Behaviors**

IRB: 18-0542
Version: 06 June 2020

[name], J.D., M.D., M.P.H.
University of Chicago
Chicago, IL

A Double-Blind, Placebo-Controlled Study of Dronabinol in Trichotillomania

This clinical trial will be conducted in the spirit of Good Clinical Practice (GCP) and in accordance with this IRB approved protocol. No deviation from the protocol will be implemented without the prior review and approval of the IRB except where it may be necessary to eliminate an immediate hazard to a research subject. In such a case, the deviation will be reported to the IRB as soon as possible.

Investigational Agent and Dosing

Dronabinol 5mg to 15mg po qday

Population

The population to be studied for this trial is 50 men and women ages 18-65 who have a current DSM-5 diagnosis of trichotillomania or other body focused repetitive behavior (BFRB) (e.g., skin picking disorder).

Project Goals

The goal of the proposed study is to evaluate the efficacy and safety of dronabinol in trichotillomania. 50 subjects with DSM-5 trichotillomania or other BFRB will receive 10 weeks of double-blind dronabinol or placebo. The hypothesis to be tested is that dronabinol will be effective and well tolerated in patients with trichotillomania or other BFRBs compared to placebo. The proposed study will provide needed data on the treatment of disabling disorders that currently lacks a clearly effective treatment.

Background

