50 individuals with trichotillomania or skin picking disorder will be recruited for a double-blind, placebo-controlled pilot study in which dronabinol or placebo is administered in a 1:1 fashion. All 50 subjects will have trichotillomania or skin picking disorder per DSM-5 criteria. Following baseline measures, all subjects will be randomized to either dronabinol or placebo and seen every 2 weeks for the first four weeks and every 3 weeks for the remainder of the 10-week period.

Participants will be started at 5mg po qday for 2 weeks, then 5mg po bid for 2 weeks and then 5mg TID for the remaining 6 weeks. Participants will only go up to the full dose if clinically needed. Efficacy and safety measures will be performed at each visit.

The study will be conducted in accordance with the International Conference on Harmonization Guideline for Good Clinical Practice, all local ethical and legal requirements, and the World Medical Assembly (Declaration of Helsinki). The study protocol and procedures will be approved by the University of Chicago's institutional review board prior to any recruitment. Written informed consent will be required for study participation.

Randomization of drug will be conducted in blocks of eight. The blind will be assessable to the study subject at all times by calling the pharmacy number listed on the medication bottle. The investigational pharmacy will follow proper accountability procedures in regards to both randomization of the study drug and holding of the blind.

Subjects:

Inclusion criteria:

- 1) men and women age 18-65;
- 2) current DSM-5 trichotillomania or skin picking disorder; and
- 3) Ability to understand and sign the consent form.

Exclusion criteria:

- 1) Unstable medical illness based on history or clinically significant abnormalities on baseline physical examination
- 2) Current pregnancy or lactation, or inadequate contraception in women of childbearing potential
- 3) Subjects considered an immediate suicide risk based on the Columbia Suicide Severity rating Scale (C-SSRS) (www.cssrs.columbia.edu/docs)
- 4) Past 12-month DSM-5 diagnosis of psychosis, major depressive disorder, bipolar disorder, mania, or a substance or alcohol use disorder
- 5) Illegal substance use based on urine toxicology screening
- 6) Stable dose of medications for at least the past 3 months
- 7) Previous treatment with dronabinol

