Although the seizure risk needs to be taken seriously, the occurrence of new seizures from dronabinol, when excluding patients with a seizure disorder, appears to be fairly low even in medically compromised patient (25). In the proposed study, our dose of dronabinol is only up to a total of 15mg each day and patients with trichotillomania are on average quite healthy. This may explain why we saw only a small amount of mild side effects in our previous study (4).

Table 1 outlines adverse events that occurred in subjects with AIDS –related anorexia and chemotherapy-related nausea as well as not medically compromised subjects with trichotillomania (4).

Table 1
Adverse events associated with dronabinol

Adverse event	Pooled trial data from studies of subjects with AIDS-related anorexia and chemotherapy-related nausea ^a	Trichotillomania study participants (n = 14)			
		2.5 mg/day (n = 14)	5 mg/day (n = 13)	10 mg/day (n = 12)	15 mg/day (n = 7)
Light-headed/dizzy	3–10%	2 (14.3%)	1 (7.7%)	1 (8.3%)	–
“High” (i.e., easy laughing, elation, and heightened awareness)	8–24%	–	1 (7.7%)	2 (16.7%)	–
Sedation	3–10%	1 (7.7%)	1 (7.7%)	–	–
Dry mouth	Frequency not specified	–	1 (7.7%)	1 (7.7%)	–
Constipation	Frequency not specified	–	1 (7.7%)	–	–
Headache	<1%	–	–	1 (7.7%)	–
Nausea/vomiting	3–10%	–	1 (7.7%)	–	–
Abdominal pain	3–10%	–	–	–	–
Paranoia	3–10%	–	–	–	–

	Pooled trial data from studies of subjects with AIDS-related anorexia and chemotherapy-related nausea ^a	Trichotillomania study participants (n = 14)			
Any side effect	Frequency not specified	3 (21.4%)	6 (46.2%)	5 (41.7%)	0

^a <http://www.fda.gov/ohrms/dockets/dockets/05n0479/05N-0479-emc0004-04.pdf>

and <http://www.merckmanuals.com/professional/lexicomp/dronabinol.html>

Subject Withdrawal

If a subject withdraws from the study, all instruments administered at the screening visit will be completed at the final visit. These will be conducted when the subject is able to come in for an early termination visit. Withdrawn subjects will be given the phone number of the principal investigator as well as the phone numbers of local resources for trichotillomania and skin picking.

Data and Safety Monitoring Plan

1. Responsibility for Data and Safety Monitoring

The PI will have overall responsibility for monitoring the integrity of study data and participant safety.

2. Procedures for Monitoring Participant Safety

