- Any moderate adverse event which appears definitely, probably, or possibly related to study participation will be reported to the University of Chicago IRB in writing within 20 working days.
- Any mild adverse event will be summarized in the IRB annual progress reports.

Statistical Analysis

Design/Randomization

The study is a double-blind, placebo-controlled study. Participants will be randomized (1:1) to receive dronabinol or placebo by the University of Chicago Investigational pharmacy in block sizes of eight, using computer-generated randomization with no clinical information.

Due to the pandemic of COVID19, study participants can perform their baseline and follow-up visits online using encrypted Zoom instead of in person visits. All inventories will be assessed. Blood samples and urine toxicology, however, will be at the discretion of the study PI. In cases where they are considered medically necessary, the participant can have them drawn locally and submitted to the study team.

Efficacy Analysis

For statistical analysis, the full-analysis set will be defined as all participants who took at least 1 dose of the study drug and had at least 1 post-randomization primary efficacy assessment. The safety-analysis set will be defined as all randomized participants who took at least 1 dose of the study drug and completed at least 1 post-randomization safety assessment. Participants with trichotillomania and skin picking disorder will be grouped as one BFRB group.

We will compare the baseline characteristics of both groups using Fisher's exact test for categorical variables and the t test for continuous variables. We will calculate adherence to treatment, based on the number of pills returned at each visit, as the number of pills taken divided by the number of days in the study $\times 100\%$.

Primary endpoint analysis

The primary outcome measure will be the change from first randomization visit to study endpoint in total composite score on the NIMH Trichotillomania Symptom Severity Scale(s) and the Sheehan Disability Scale.

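### The adherence formula divides pills taken by days in the study, which is right only at one pill a day; with dosing that rises to three times daily, the score mixes adherence with dose reached and time in study.

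*Combined protocol and SAP*

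**What the plan says.** Under Statistical Analysis, Efficacy Analysis, the plan takes its pill count from returns, "based on the number of pills returned at each visit", and defines adherence "as the number of pills taken divided by the number of days in the study", multiplied by 100%. The number of pills prescribed does not enter the formula. No other adherence definition, dose adjustment or cap appears in the document.

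Under Methodology, the schedule is "5mg po qday for 2 weeks, then 5mg po bid for 2 weeks and then 5mg TID for the remaining 6 weeks". The next sentence makes escalation conditional: "Participants will only go up to the full dose if clinically needed". The Safety Assessments section is consistent with this maximum: "our dose of dronabinol is only up to a total of 15mg each day". Under Project Goals, the 50 subjects "will receive 10 weeks of double-blind dronabinol or placebo".

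The opening page, under Investigational Agent and Dosing, gives a different frequency: "Dronabinol 5mg to 15mg po qday".

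**The concern.** Dividing by days treats one pill a day as full adherence. On the Methodology schedule that holds only for the first two weeks, or for a participant who stays at the starting dose. After that, the score of a perfect adherer depends on how far that participant was titrated.

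A constant inflation would be harmless, because everyone would be rescaled alike. Here the factor differs between participants, since escalation depends on clinical need, and it also changes with time in the study.

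The stake is interpretive. In a 50-person trial, a small or null effect raises the question of whether participants took the drug. As written, the figure could show substantial non-adherence as 100% or more. It could also show a difference between arms that reflects titration alone.

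**Working it through.** The plan states no adherence value, target or threshold, so there is no figure to reproduce. The check applies the plan's own formula to its own schedule.

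**Inputs**
- Phases (Methodology): 14 days at one dose a day, 14 days at two, 42 days at three. 14 + 14 + 42 = 70 days, which agrees with the 10 weeks under Project Goals.
- Formula (Efficacy Analysis): score = pills taken / days in the study × 100%.
- Assumptions: one 5 mg pill per scheduled dose, with 2.5 mg pills as the alternative, because strength is not stated; days in the study counted as the 70 treatment days; either dose increase may be withheld.

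**Perfect adherence over 70 days**

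| Dose path | Pills due | Score, one pill per dose | Score, 2.5 mg pills |
|---|---|---|---|
| 5 mg/day throughout | 14 + 14 + 42 = 70 | 70/70 = 100% | 200% |
| Held at 10 mg/day | 14 + 28 + 84 = 126 | 126/70 = 180% | 360% |
| Full titration | 14 + 28 + 126 = 168 | 168/70 = 240% | 480% |

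**Share of doses that scores 100% (one pill per dose)**
- Full titration: 70/168 = 41.7%.
- Held at 10 mg/day: 70/126 = 55.6%.

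A fully titrated participant who takes half the doses scores 0.5 × 168/70 = 120%, above a perfect adherer kept at 5 mg. If only the last increase is optional, the problem remains: a fully titrated participant taking 126/168 = 75% of doses scores 180%, the same as a perfect adherer held at 10 mg/day.

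**Time in study.** Visits fall at weeks 2, 4, 7 and 10. For a perfect adherer on the full schedule:
- By interval, the scores are 100%, 200%, 300% and 300%.
- Leaving at week 2: 14/14 = 100%.
- Leaving at week 4: 42/28 = 150%.
- Leaving at week 7: 105/49 = 214%.

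**Between arms (mechanism only; the rates are assumed, not taken from the plan).** Suppose 80% of one arm and 50% of the other reach three times daily, the rest are held at 10 mg/day, and all adhere perfectly. The mean scores are 0.8 × 240 + 0.2 × 180 = 228% and 0.5 × 240 + 0.5 × 180 = 210%.

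**With pills prescribed as the denominator,** perfect adherence scores 100% on every path: 70/70, 126/126 and 168/168.

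**The case against.** The strongest objection concerns consequence. Adherence is only calculated. There is no per-protocol set, adherence threshold or planned test of adherence between arms. Both analysis sets require one dose and one assessment, and neither the primary nor the secondary models mention adherence. This stands: no planned efficacy or safety result changes.

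A second objection is that the once-daily line on the opening page could rescue the formula. It would do so only if every dose level were a single pill. With 5 mg pills, 10 mg and 15 mg once daily still mean two and three pills a day, so the scores in the working are unchanged. The conflict between the two sections is nonetheless real.

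A third is that arm-level values near 200% would reveal the error at once. That is likely for arm means, but less so for an individual score near 100%. The analyst would then also have to choose a replacement formula after the data are in.

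A reader might infer several stronger things that the documents do not support:
- *That the score measures dose instead of adherence.* On any one dose path it remains proportional to adherence; it mixes the two.
- *That 240% is the most the formula can give.* It depends on one pill per dose; with 2.5 mg pills the full schedule gives 480%.
- *That this is the trial's only exposure measure.* The documents do not establish this; prescribed dose, if recorded, would be another.
- *That the arms will titrate differently.* Conditional escalation permits it, but the plan gives no rates.

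**Conclusion.** The formula is wrong as written for the schedule in the Methodology section, and nothing elsewhere in the document corrects it. At one pill per scheduled dose, perfect adherence is reported as 100%, 180% or 240% depending on the dose path. The exact values rest on the unstated pill strength and on counting 70 treatment days. The defect itself does not: each scheduled dose needs at least one pill, so a perfect adherer on the full schedule cannot score below 240%.

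The resulting figure should not be read as adherence, or compared between participants or arms with different titration. The damage is confined to that figure and to any interpretation built on it. It gives no reason to doubt the planned efficacy comparison itself.

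**What to change.** Replace the definition with: pills taken (dispensed minus returned) divided by pills prescribed to that participant over the same interval, × 100%. Take the prescribed count from the dose level actually assigned between visits, including any change within an interval. Report it by visit interval and overall, by arm.

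Two related edits are needed:
- Reconcile the dosing line on the opening page with the Methodology schedule, and state the pill strength and pills per dose, so that the prescribed count is unambiguous.
- State how returned pills are counted when visits are held online. The plan allows such visits but does not cover this.

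The cost is a sentence or two of wording. The calculation needs dispensing counts and assigned dose by interval. The Data Management Plan's list of collected data mentions neither, so confirm that pharmacy or visit records hold them. If they do, no new data collection is needed.

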Given the serious personal consequences associated with trichotillomania and skin picking disorder, and the likelihood of success of dronabinol in treating both disorders, the aim of the present study was to examine the efficacy and safety of dronabinol vs placebo in adults with trichotillomania or skin picking disorder using a double-blind, placebo-controlled design.

We hypothesize that dronabinol will be more effective than placebo in reducing the frequency of hair pulling and skin picking and in improving overall psychosocial functioning after 10 weeks of treatment when compared to baseline.

Primary Aim/Objective

The aim of the present study is to examine the efficacy and safety of dronabinol vs placebo in adults with trichotillomania and skin picking disorder.

Co-Primary Endpoint(s):

The co-primary efficacy measures will be the change in hair pulling or skin picking frequency and urges to pull hair or pick skin for the past week as indicated by change in total score on the *NIMH Trichotillomania Symptom Severity Scale* (for TTM) or *Skin Picking Symptom Assessment Scale* (for SPD), reliable and valid clinician-administered measures (18-19), as well as the same scale modified for skin picking disorder, and the change in psychosocial functioning over the same time period using the *Sheehan Disability Scale* (20). The co-primary efficacy end points will be the change in these measures from baseline to week 10.

Secondary Aim/Objective

A secondary aim of the study is to examine the effects of dronabinol vs placebo on self-report measures of hair pulling, skin picking, quality of life, and measures of mood and anxiety.

Secondary Endpoint(s):

Secondary efficacy measures include the change in number of days per week pulling, the *Clinical Global Impressions–Improvement Scale* (CGI-I) rated global improvement of symptoms over time (results will be dichotomized as improved [CGI-I ratings of 1 or 2 very much/much improved] or not improved [CGI-I ratings of 3-7]) (20), the self-report *Massachusetts General Hospital Hairpulling Scale* (22), the *Skin Picking Symptom Assessment Scale*, the *Quality of Life Inventory* (23), the *Hamilton Depression Rating Scale* (24), the *Hamilton Anxiety Rating Scale* (25), and the *Tridimensional Personality Questionnaire*

Methodology

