- 8) Cognitive impairment that interferes with the capacity to understand and self-administer medication or provide written informed consent

Baseline Assessments:

Those subjects who appear appropriate for the study, based on telephone screening, will be invited for a baseline assessment. The duration of the baseline assessment will be approximately 90 minutes and will include the following: informed consent, demographic data, concomitant medications (no psychotropic medications will be allowed), and family history data. There will also be a physical examination (including weight, and vital signs, urine pregnancy test for women of childbearing years and urine drug screen, as well as a baseline blood draw to assess nutritional status. The blood draw is optional to the subject and will administered at the PI's discretion). Finally, the subjects will undergo a psychiatric evaluation (using the MINI International Neuropsychiatric Interview).

In addition, the following instruments will be completed at the screening visit: 1) NIMH Trichotillomania Symptom Severity Scale (or the same scale modified for skin picking); 2) Sheehan Disability Scale; 3) Massachusetts General Hospital Hairpulling Scale; 4) the 17-item

Hamilton Rating Scale for Depression (HAM-D); 5) the 17-item Hamilton Rating Scale for Anxiety (HAM-A); 6) Clinical Global Impression (Improvement and Severity) scale; 7) Cambridge Caffeine Use Questionnaire; 8) The Dietary Fat and Free Sugar Questionnaire and 9) the Quality of Life Inventory; 10) Cambridge-Chicago Trait Scale (12); the Skin Picking Symptom Assessment Scale (SP-SAS); and the Body Focused Repetitive Behavior Broad Assessment Measure (BFRB-BAM), a new scale being added for validation purposes. In addition, subjects will undergo cognitive assessments at baseline and study endpoint.

Cognitive Assessments: Assessments of cognitive control will be comprised of several valid paradigms (See below). These tasks are designed to probe dissociable neural circuitry and cognitive processes likely to be implicated in the pathophysiology of addictions. Task order was chosen arbitrarily and will be applied consistently across subjects, to minimize possible confounding factors of differences in task order across participants.

The following tasks will be administered at baseline and final visits:

- Stop Signal Task of Inhibitory Control (SST)
- Intra-dimensional/Extra-dimensional Set Shift Task (ID/ED task)
- One Touch Stockings Task (OTS)

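### The primary endpoint is defined inconsistently: two co-primary end points in one section, one composite score in another, two candidate primary scores for skin picking, and no success rule

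*Combined protocol and SAP*

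**What the plan says.** **Number of end points.** The Background section hypothesises that dronabinol will beat placebo "in reducing the frequency of hair pulling and skin picking and in improving overall psychosocial functioning". The Co-Primary Endpoint(s) section pairs a symptom score with the Sheehan Disability Scale and states: "The co-primary efficacy end points will be the change in these measures from baseline to week 10". Under Statistical Analysis, the Primary endpoint analysis section names a single primary outcome, the change in "total composite score on the NIMH Trichotillomania Symptom Severity Scale(s) and the Sheehan Disability Scale". The Sample Size section refers to a co-primary endpoint in the singular without saying which.

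**Skin-picking score.** The Co-Primary Endpoint(s) section assigns the NIMH scale to trichotillomania and the Skin Picking Symptom Assessment Scale (SP-SAS) to skin picking disorder. It calls them "reliable and valid clinician-administered measures" and then adds "as well as the same scale modified for skin picking disorder". The Secondary Endpoint(s) section lists the SP-SAS again. The Primary endpoint analysis section names only the NIMH scale(s). The Secondary endpoints analyses section treats the SP-SAS as a self-report secondary. Baseline Assessments collects both the NIMH scale ("or the same scale modified for skin picking") and the SP-SAS, and the follow-up visits repeat the psychiatric measures.

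**Pooling.** Under Efficacy Analysis: "Participants with trichotillomania and skin picking disorder will be grouped as one BFRB group".

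**The concern.** Two co-primary end points and one composite are different hypotheses with different success criteria. With two end points the plan must say whether both or either must succeed; with a composite it must say how the scales are combined. It does neither. The hypothesis joins symptoms and functioning with an and, which leans towards requiring both, but no section turns that into a decision rule.

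The skin-picking problem is separate. One instrument is both primary and secondary, and both clinician-administered and self-reported, while a second instrument competes for the primary role. Because the diagnoses are pooled, that choice changes the data entering the single primary ANOVA.

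At stake is the trial's verdict: the same data can succeed under one section and fail under another, with the choice open after the results are known.

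**Working it through.** **1. The plan's own figure.** Inputs from Sample Size: 80% power, effect size d = 0.5, two-group t test at .05. Normal approximation: n per arm = 2(z_α + z_0.80)² / d².
- One-sided: 2(1.645 + 0.842)² / 0.25 = 49.5, so 50 (exact t: 50.15).
- Two-sided: 2(1.960 + 0.842)² / 0.25 = 62.8, so 63 (exact t: 64).

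The stated 50 per group is reproduced only one-sided. Since sidedness is not stated, both versions are shown below.

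**2. The sections side by side.**

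| Section | Primary end points | SP-SAS |
|---|---|---|
| Co-Primary Endpoint(s) | Two: symptom score; Sheehan | Primary, clinician-administered; modified NIMH scale added |
| Secondary Endpoint(s) | – | Secondary |
| Baseline Assessments | – | Collected, as is the modified NIMH scale |
| Primary endpoint analysis | One composite, no scoring | Not named |
| Secondary endpoints analyses | – | Secondary, self-report |
| Sample Size | One, not identified | – |

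**3. How much the success rule matters.** Inputs: 25 per arm (Methodology: 50 in total, 1:1) and d = 0.5. Assumed, because the documents are silent: d = 0.5 on both measures, correlation ρ between the two changes of 0 / 0.5 / 0.8, and a composite equal to the sum of the two changes, each divided by its blinded SD.

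- Single measure: noncentrality 0.5 × √(25/2) = 1.77 on 48 df; power 41% two-sided, 54% one-sided.
- Both must win, ρ = 0: 0.410² = 0.168 two-sided; 0.539² = 0.291 one-sided. Other values of ρ by simulation.
- Composite: d_c = 1/√(2 + 2ρ) = 0.707 / 0.577 / 0.527.

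| ρ = 0 / 0.5 / 0.8 | Two-sided .05 | One-sided .05 |
|---|---|---|
| Both must win | 17 / 25 / 31% | 29 / 37 / 43% |
| Composite | 69 / 52 / 45% | 79 / 64 / 57% |
| Opposite verdicts | 52 / 27 / 14% | 50 / 27 / 14% |

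Two-sided, the disagreement is the composite rate minus the both-must-win rate (0.686 − 0.168 = 0.518; 0.516 − 0.246 = 0.270; 0.446 − 0.308 = 0.138). This works because both measures winning while the composite fails occurs in at most 0.0001 of trials. Simulated entries carry up to about one point of noise.

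**4. Choosing the rule afterwards (two-sided).** If the drug affects neither measure, declaring success when either both-must-win or the composite succeeds has error 5.1 / 5.0 / 4.9%. If it affects Sheehan only (d = 0.5, symptom d = 0), the same choice declares success in about 23 / 16 / 14% of trials, although a claim on both measures is then false.

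**5. Choosing the skin-picking score afterwards (two-sided).** Assumed: skin-picking share 30–70% and correlation between the two skin-picking scores 0.5–0.8, with the trichotillomania score fixed. Taking the better result gives null error on the symptom test of about 6.6–8.7%. With d = 0.5 on both scores, the symptom verdict differs between them in 11–27% of trials.

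**The case against.** The strongest defence is that the composite wording may loosely mean a total score on each of two scales. The ANOVA is specified for continuous measures in the plural, so the plan would then run as two ANOVAs and the sections would agree on two measures. This reading is possible. A reader might infer that the primary analysis cannot be run as written; because of this reading, the documents do not support that. It still leaves no success rule or sidedness, and it does not touch the skin-picking conflict.

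A reader might also infer that the plan itself inflates type I error. An unadjusted either-wins rule would give 9.6 / 9.1 / 7.8% two-sided, but no section states such a rule. Both-must-win, or one composite, fixed in advance, holds .05 for its own claim. The opposite inference, that choosing between those two afterwards is harmless, is also unsupported: it holds only if the drug affects neither measure.

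It is fair that the disagreement figures need a standardised composite and a both-must-win rule that the plan does not state, and that the 52% end needs zero correlation between symptom and disability change. It is also fair that the low power partly reflects a separate conflict between 50 participants in total and 50 per group. At 50 per group, both-must-win would reach about 50 / 56 / 62% two-sided (normal approximation).

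The Methodology section calls the study a pilot, but Project Goals states an efficacy hypothesis to be tested, so a defined primary test is needed.

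**Conclusion.** The concern holds as an inconsistency in definition. The plan contradicts itself on the number of primary end points if the composite wording is taken at face value, and on the role and type of the SP-SAS under any reading. It states no success rule or sidedness.

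The choice of rule alone reverses the verdict in about 14–52% of trials two-sided, or 14–50% one-sided. The choice of skin-picking score reverses the symptom verdict in about 11–27%. These ranges rest on 25 per arm, d = 0.5 throughout, and the assumed correlations, diagnosis mix and composite form. The textual conflict rests on none of them. Confidence in the conflict is high; the percentages are illustrative.

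**What to change.** Before unblinding:

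1. **Name one primary symptom score per diagnosis**, with a baseline rule for anyone who has both disorders, and use it consistently in Co-Primary Endpoint(s), Secondary Endpoint(s), Primary endpoint analysis, Secondary endpoints analyses and Sample Size. For skin picking there are two defensible choices.
   - The modified NIMH scale fits Baseline Assessments and the Primary endpoint analysis, and keeps the SP-SAS secondary. The plan makes no separate validity statement for it.
   - The SP-SAS fits its assignment to skin picking disorder in Co-Primary Endpoint(s) and the validity statement there. It must then leave the secondaries, and the pooled analysis needs a pre-stated common metric.
2. **Delete the composite wording and state one success rule and sidedness that hold error at .05.** Both-must-win matches the hypothesis. A fixed sequence (symptom score, then Sheehan) or Holm are alternatives. State the resulting power at the actual sample size.

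The cost is wording only, since both instruments are already collected. The downside is less favourable stated power. At 25 per arm, d = 0.5 and ρ = 0 / 0.5 / 0.8:
- Both-must-win: 17 / 25 / 31% two-sided, or 29 / 37 / 43% one-sided.
- Fixed sequence, two-sided: 41% for the symptom claim, with Sheehan claimable in 17 / 25 / 31%.
- Holm, two-sided: at least one claim in 51 / 45 / 39%, both in 16 / 23 / 29%.

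The conflict between 50 in total and 50 per group must be resolved separately before a final power can be stated.
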